2.5.4 Description of the Investigational Device (Tendyne Mitral Valve System)

The Tendyne Mitral Valve is a bioprosthetic valve, which consists of a porcine pericardial tri-leaflet valve attached to an inner frame. This inner valve is then attached to an outer frame and a tether. During the implantation procedure, the tether is secured to an apical pad on the epicardial surface of the heart.

The inner valve is comprised of three (3) identical, porcine leaflets assembled onto a circular, self-expanding inner frame. The outer valve assembly is intended to provide sealing and conform to the native mitral annulus. It is made from the same super-elastic nickel-titanium alloy (Nitinol) as the inner frame. The outer surface of the outer-frame is covered with a porous polyester material. The atrial surface of the outer-frame is covered in fixed porcine pericardial tissue. The inner porcine and outer polyester materials are sutured to the outer frame with braided ultra-high molecular weight polyethylene suture.

A radiopaque marker at A1 can be visualized under fluoroscopy to confirm orientation of the valve. The outer-frame cuff is raised along the straight leg of the D-shape frame and is referred to as the A2 region or the “proud cuff” as it is the tallest section of the outer frame. The proud cuff of the outer-frame is also used to orient the prosthesis inside the native mitral valve.

The valve is fully repositionable and retrievable intraoperatively. Repositioning allows optimization of the valve position following deployment, and retrieval allows use of an alternative valve size if the initial valve does not have adequate performance.

The inner valve is assembled into various sizes of outer frames to give the valve the ability to conform to a wide range of patient geometries. The size of the valve is defined by the anterior-posterior (AP) length, inter-commissural diameter (IC), the perimeter (PER) of the outer-frame and the effective orifice area (EOA). Imaging techniques are used to determine valve size based on the subject’s mitral annulus dimensions. The valve size is chosen to provide the proper fit for paravalvular sealing and device stability. The decision regarding which valve size to implant may be influenced by the simulated area of the LVOT created following implantation of the valve. This modeling is performed using software (Circle cardiovascular imaging software, www.circlecvi.com; and Mimics medical image segmentation for engineering on anatomy, biomedical.materialise.com/mimics).

The Instrument Set used in the transapical implantation of the valve includes the following components: 1) Tendyne Loading System, 2) Tendyne Delivery System and 3) Tendyne Pad Positioning System. An additional instrument 4) Tendyne Retrieval System, is also available, which can be used to retrieve the valve intraoperatively, should the valve implant be suboptimal. All of the components of these systems are provided sterile via ethylene oxide (EO) sterilization. All components of these systems that come in contact with the subject are also provided non-pyrogenic.

For a more detailed description of the Tendyne Mitral Valve System refer to the Instructions for Use (IFU).

2.5.5 Procedures Involved in the Use of the Device

The procedures outlined in the approved Tendyne Mitral Valve System IFU must be followed in the use of this device under this CIP.

2.5.6 Training Required for the Use of the Device

Investigators will be trained in accordance with the approved Tendyne Mitral Valve System IFU. Investigator training will include, but will not be limited to, the use of a bench top model and demonstration unit to ensure that investigators understand the mechanics and characteristics of the Tendyne Mitral Valve System. Sponsor staff will conduct this training and a training log will be used for documentation. Only physicians who receive all required device training and have documentation that training was completed can perform the Tendyne procedure under this CIP.

2.5.7 Investigational Device Accountability

The Sponsor is responsible for the availability and distribution of all investigational products. Product will only be distributed to study sites when the Sponsor has provided written documentation of investigational site readiness. The Sponsor will ship and/or hand-carry devices

(the Tendyne System) to the Principal Investigator or his/her designee at each site. The Tendyne System must be stored in a secured location separate from market-released products.

The investigator, or designee, will maintain adequate records of the receipt and disposition of the investigational device system, including reference/serial/lot numbers (as appropriate), date of use, subject number and implanting physician(s). A Device Accountability Log supplied by the Sponsor will be used. All unused investigational devices must be returned to the Sponsor when study registration is complete (completed device accountability reports will be generated for the site) or as otherwise deemed necessary (e.g., expired devices).

Any investigational devices that are associated with a device failure or device deficiency (and were not successfully implanted) should be returned immediately to the Sponsor.

3 STUDY OBJECTIVES / ENDPOINTS

The objective of this study is to capture preliminary information regarding the safety and effectiveness of the Tendyne Mitral Valve System. There are no pre-defined pass or fail criteria for evaluating the study objectives. Endpoints were selected to help determine the feasibility of the Tendyne Mitral Valve System in the treatment for mitral regurgitation in subjects with MAC.

3.1 Primary Safety Endpoint

The primary safety endpoint will evaluate the procedural and device safety of the Tendyne Mitral Valve System. The composite endpoint is: Device Success (defined below) and freedom from device or procedure related serious adverse events (SAEs) at 30 days post implant, as classified by the Clinical Events Committee (CEC).

Definition of Device Success:

All of the following must be present:

- 1) Absence of procedural mortality or stroke; and
- 2) Proper placement and positioning of the device, and
- 3) Freedom from unplanned surgical or interventional procedures related to the device or access procedure; and
- 4) Continued intended safety and performance of the device, including:
 - a) No evidence of structural or functional failure
 - b) No specific device-related technical failure issues or complications
 - c) Reduction of MR to either optimal or acceptable levels without significant structural valve dysfunction and with no greater than mild (1+) paravalvular MR (and without associated hemolysis).

Structural failure is when the valve fails to perform as intended due to a complication related the valve, such as: fracture, migration or embolization. Functional failure is when the valve performs as intended without complication but does not adequately reduce the degree of MR or results in new, significant mitral stenosis.

Post-procedure MR reduction is considered optimal when reduced to trace or absent and acceptable when reduced by at least 1 class or grade from baseline and to no more than moderate (2+) residual MR in severity [25].

Note: Criterion #4c above has been modified from the MVARC guidelines [25], to align with the structural valve dysfunction definition used in this CIP.

3.2 Clinical Endpoints

The following clinical endpoints will be evaluated:

- Technical success evaluated upon exit from procedure room, defined as:
 - 1) Absence of procedural mortality; and
 - 2) Successful access, delivery and retrieval of the device delivery system; and
 - 3) Successful deployment and correct positioning of the intended device; and
 - 4) Freedom from emergency surgery or re-intervention related to the device or access procedure
- Patient Success evaluated at 1, 2, 3, 4, and 5 years post index procedure, defined as:
 - 1) Device Success (either optimal or acceptable); and
 - 2) Subject returned to the pre-procedural setting (e.g. home, assisted living facility); and
 - 3) No transcatheter or surgical re-interventions for mitral valvular disease (modified from MVARC guidelines); and
 - 4) Improvement from baseline symptoms (NYHA improvement by ≥ 1 Functional Classification); and
 - 5) Improvement from baseline in functional status (6MWD improvement by ≥ 50 meters); and
 - 6) Improvement from baseline in Quality of Life (KCCQ improvement by ≥ 10 points)
- Device Success as measured at 30 days and at all post-procedural intervals
- Freedom from all-cause mortality at 3 months, 6 months, 1 year, and then annually through 5 years post index procedure
- Distance walked on the 6MWT at baseline, 30 days, 3 months, 6 months, 1 year, and then annually through 5 years post index procedure (change from baseline to follow-up)
- KCCQ QoL scores at baseline, 30 days, 3 months, 6 months, 1 year, and then annually through 5 years post index procedure (change from baseline to follow-up)
- NYHA Functional Classification at baseline, 30 days, 3 months, 6 months, 1 year, and then annually through 5 years post index procedure

4 STUDY DESIGN, SCOPE AND DURATION

4.1 Study Design

This study is a prospective, single-arm, multicenter feasibility clinical study of the Tendyne Mitral Valve System for the treatment of eligible subjects with symptomatic, severe mitral regurgitation and severe mitral annular calcification (MAC).

Subjects whom the local site heart team determines: (a) are not suitable candidates for conventional mitral valve surgery due to the degree of MAC present; (b) will likely benefit from transcatheter valve implantation; and (c) meet study entrance criteria will receive the Tendyne device.

4.2 Number of Subjects to be Registered

This study will enroll male and female subjects who satisfy the inclusion and exclusion criteria and provide written informed consent. This study will register up to 30 subjects at up to 10 investigational sites in the U.S.

Subjects are enrolled in the study upon signing the informed consent form. Subjects are considered registered in the study upon attempt of the implant procedure.

There is no minimum number of subjects to be registered at any site.

4.3 Total Expected Duration of the Clinical Investigation

The total duration of the study is estimated as 76 months. This includes a 16-month subject enrollment phase period, with subject follow-up continuing for an additional 60 months.

Subjects will have required follow-up evaluations at pre-discharge, 30 days, 3 months, 6 months, 1 year, and then annually through 5 years post index procedure (see **Table 2** for visit windows). When all registered subjects have been followed for 5 years, or have exited the study, the study will be closed.

5 SUBJECT SELECTION AND WITHDRAWAL

5.1 Subject Screening and Informed Consent

All subjects must be screened by the site's investigator and clinical research staff, who have been trained to the CIP, to determine if the potential subject is eligible for study registration. Potential subjects will be assigned a unique subject identifier through the electronic Case Report Form (eCRF) database.

Patients are enrolled (i.e., become "subjects") after they sign the Informed Consent Form (ICF). During the informed consent process, the investigator or designee, who has been trained on the CIP, will explain the nature and scope of the study, potential risks and benefits of participation, and answer questions from potential subjects. All subjects (or subjects' legally authorized representatives, if applicable) must sign and date the IRB approved informed consent form prior to any clinical study-specific procedures. No subjects belonging to a vulnerable population (see **Appendix II: Definitions**) will be enrolled.

Obtaining the consent, and provision of a copy of the consent to the subject, along with date and time must be documented in the subject's medical records. The informed consent form must be signed by the investigator (or designee). In addition, the signed informed consent must be kept in the subjects medical records. The investigator, or designee, is responsible for advising the subject of any new information about the investigation or the Tendyne device that may become known during the study.

If a specific test required to determine a subject's eligibility is not standard of care, the test must be performed after written informed consent has been obtained. If any of the required screening assessments are conducted as part of standard of care prior to obtaining written informed consent, it is acceptable to provide the results of these previously performed tests for purposes of screening after the subject (or subject's legally authorized representative) has provided informed consent.

An authorization for use and disclosure of the subject's protected health information, in accordance with the Health Insurance Portability and Accountability Act (HIPAA), must be obtained from the subject or the subject's legally authorized representative.

For live cases at congresses, subjects need to sign a specific Live Case ICF, approved by the IRB and by Tendyne Holdings, Inc., as well as by the regulatory authorities (e.g. FDA), as applicable. The investigator must request Tendyne Holdings, Inc. approval prior to performing a Live Case.

5.1.1 Enrollment of Medicare Beneficiaries

This clinical investigation will enroll appropriate Medicare beneficiaries that qualify based on the inclusion and exclusion criteria set forth in the study. The investigational device exemption (IDE) clinical trial adheres to all standards of Medicare coverage requirements set forth by CMS's IDE and clinical trial coverage policies. The Risk Analysis section of this CIP (see **Section 16**) describes how all enrolled subjects, including Medicare beneficiaries, may be affected by the device under investigation.

Subjects enrolled in the clinical investigation are expected to be consistent with the Medicare population based on demographic characteristics and cardiovascular risk factors, therefore, the clinical investigation results are expected to be generalizable to the Medicare population.

5.2 Eligibility Criteria

5.2.1 General Eligibility Criteria

Assessment for general eligibility criteria is based on medical records at the site and interview with a potential subject. Clinical and laboratory tests used to assess eligibility shall be per site standard. If a specific test required to determine subject's eligibility is not included in a site's standard tests, the test must be performed after written informed consent has been obtained from the subject (or the subject's legally authorized representative, if applicable).

If any of the required screening assessments are conducted as part of standard of care prior to obtaining written informed consent, it is acceptable to provide the results of these previously performed tests for purposes of screening after the subject (or subject's legally authorized representative) has consented to participate in the study. Subjects must meet all of the inclusion criteria to be considered for the clinical study. If any of the exclusion criteria are met, the subject is excluded from the clinical study and cannot be registered.

5.2.2 Inclusion Criteria

Patients must meet all of the following inclusion criteria to participate in the study:

1. Heart Team determines subject is not a suitable candidate for conventional surgical treatment due to degree of MAC present and the subject will likely benefit from transcatheter valve implantation
2. Symptomatic, severe mitral regurgitation, as defined in the 2017 ACC expert Consensus Decision Pathway on the Management of MR (see **Figure 1** in the Appendix II)
3. NYHA Functional Classification \geq II (if Class IV, patient must be ambulatory)
4. Age 18 years or older at time of consent
5. Not a member of a vulnerable population per the investigator's judgment
6. The subject or the subject's legal representative has been informed of the nature of the study and agrees to its provisions, including complying with study required testing and follow-up visits, and has provided written informed consent

5.2.3 *Exclusion Criteria*

Subjects must not meet any of the following exclusion criteria to participate in the study:

1. Presence of Left Ventricle or Left Atrium thrombus
2. Chest condition that prevents transapical access
3. Left Ventricular Ejection Fraction (LVEF) less than 25% assessed by echocardiogram
4. Left Ventricular End Diastolic Dimension (LVEDD) > 7.0 cm
5. Severe mitral stenosis not amenable to balloon valvuloplasty or transcatheter therapy
6. Prior intervention with permanently implanted mitral device (e.g. MitraClip)
7. Mitral pathoanatomy and Left Ventricular Outflow tract (LVOT) anatomy deemed not suitable for Tendyne mitral valve implantation
8. Any planned cardiac surgery or intervention that is 30 days prior and 30 days post that is not concomitant with the Tendyne procedure
9. Cardiac resynchronization therapy (CRT) device or implantable pulse generator (IPG) implanted within three months of planned implant procedure
10. Myocardial Infarction (MI) within 30 days of the planned implant procedure
11. Symptomatic, or ischemia-associated coronary artery disease (e.g., active ischemia) amenable to revascularization and thus requiring stenting or CABG
12. Cerebrovascular accident (CVA) within six months of planned implant procedure
13. Unresolved severe symptomatic carotid stenosis (> 70% by ultrasound)
14. Cardiogenic shock or hemodynamic instability requiring inotropes or mechanical support devices within 1 month prior to planned implant procedure
15. Severe tricuspid regurgitation or severe right ventricular dysfunction
16. Hypertrophic or restrictive cardiomyopathy, constrictive pericarditis or any other structural heart disease causing heart failure other than dilated cardiomyopathy of either ischemic or non-ischemic etiology
17. Any of the following: leukopenia, acute anemia, thrombocytopenia, history of bleeding diathesis, or coagulopathy if cannot be adequately treated
18. History of endocarditis within 6 months of planned implant procedure
19. Active systemic infection requiring antibiotic therapy
20. Known hypersensitivity or contraindication to procedural or post-procedural medications (e.g., contrast solution, anti-coagulation therapy) which cannot be adequately managed medically
21. Subject unable or unwilling to take anticoagulation with warfarin for a minimum of 6 months following Tendyne valve implantation
22. Known hypersensitivity to nickel or titanium

23. Subject is undergoing hemodialysis due to chronic renal failure (\geq Stage 4 CKD)
24. Subject has pulmonary arterial hypertension (fixed PAS >70 mmHg)
 - a. **Note:** If PAS > 70 mmHg, site must provide documentation PAS is not fixed in order to be eligible
25. FEV1 $< 50\%$ of predicted **or** < 1 L
26. Subject refuses blood transfusions
27. Subject has COPD requiring continuous home oxygen therapy or chronic outpatient oral steroid use
28. Pregnant, lactating, or planning pregnancy within next 12 months
 - a. **Note:** Female subjects of childbearing age should be instructed to use safe contraception (e.g. intrauterine devices, hormonal contraceptives: contraceptive pills, implants, transdermal patches hormonal vaginal devices, injections with prolonged release).
29. Currently participating in an investigational drug or another device trial that has not reached its primary endpoint
 - a. **Note:** Trials requiring extended follow-up for products that were investigational, but have since become commercially available, are not considered investigational trials.
30. Subjects with non-cardiac co-morbidities that are likely to result in a life expectancy of less than 12 months

5.3 Subject Discontinuation

Each registered subject shall remain in the study until completion of the required follow-up period, however, a subject's participation in any clinical study is voluntary and the subject has the right to withdraw at any time without penalty or loss of benefit. Conceivable reasons for discontinuation may include, but not be limited to, the following:

- Subject death
- Subject voluntary withdrawal
- Subject lost-to-follow-up as described below
- Subject's follow-up is terminated according to **Section 5.4 - Early Termination of the Clinical**

The Sponsor must be notified of the reason(s) for subject discontinuation. The site will provide this information to the Sponsor. Investigators must also report this to their respective IRB as defined by their institution's procedure(s).

No additional follow-up will be required or data recorded from subjects once withdrawn from the study, except for the status (deceased/alive), which will be obtained from the Social Security Death Index.

However, if a subject withdraws from the study due to problems related to the safety or performance of the investigational device, the investigator shall ask for the subject's permission to follow his/her status/condition outside of the clinical investigation.

5.3.1 *Subject Lost-to-Follow-up*

If a subject misses two consecutive required follow up visits and attempts to contact the subject as detailed below are unsuccessful, then the subject is considered lost to follow-up. Site personnel shall make all reasonable efforts to locate and communicate with the subject (and document these efforts in the source documents), including the following:

- A minimum of two (2) telephone calls, or e-mails, on different days over the specified follow-up window to contact the subject should be recorded in the source documentation, including date, time and initials of site personnel trying to make contact.
- If these attempts are unsuccessful, a certified letter should be sent to the subject.
- If a subject misses one or more non-consecutive follow-up visits it will be considered a missed visit. The subject may then return for subsequent visits. If the subject misses two consecutive time points and the above-mentioned attempts at communicating with the subject are unsuccessful, the subject will be considered lost-to-follow-up.

Note: Contact with a general practitioner, non-study cardiologist or relative without presence of subject, or indirect documentation obtained via discharge letters will not be considered subject contact.

5.4 **Early Termination of the Clinical Study**

No formal statistical rule for early termination of the study for insufficient effectiveness of the investigational device is defined.

The Sponsor reserves the right to discontinue the clinical study/investigation at any stage or reduce the follow up period with suitable written notice to the investigator. Possible reason(s) may include, but are not limited to:

- Unanticipated adverse device effect (UADE) occurs and it presents an unreasonable risk to the participating subjects
- Recommendation from the Data Safety Monitoring Board (DSMB) and Steering Committee decision to terminate the study
- Further product development is cancelled
- Decision by a regulatory body

Should the clinical study be discontinued by the Sponsor, subjects will be followed per routine hospital practice, with device-related AEs being reported to the Sponsor. The investigator shall return all clinical study/investigational materials (including devices) to the Sponsor, and provide written notification to the overseeing IRB (if applicable) regarding reasons for premature termination. All applicable Clinical Investigation documents shall be subject to the same retention policy as detailed in **Section 13 – Data Handling and Record Keeping**.

5.5 **Study Completion**

The study will be completed when all registered subjects have either completed a 5 year follow-up visit, have reached a clinical outcome or have withdrawn from the study. Upon study completion, the Sponsor and/or its designees will notify the sites and perform study closeout visits.

All unused devices and any unused study materials and equipment will be collected and returned to the Sponsor and/or its designees. The Sponsor and/or its designees will ensure that the investigator's regulatory files are up to date and complete, that database queries are resolved, and that any outstanding issues from previous monitoring visits have been resolved.

Other items that will be reviewed during the study closeout visit may include: discussing record retention requirements, device accountability, the possibility of site audits, publication policy, and notifying the IRB of study closure.

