10.2.7 Analysis of Clinical Endpoints

Definition of clinical endpoints are described in **Section 3.2**.

For composite endpoints, i.e., technical success, patient success, and device success, the number and percentage of subjects with success will be summarized. Descriptive statistics for components of each endpoint will also be provided.

For continuous variables (e.g., KCCQ scores and 6MWT distances), results will be summarized with the numbers of observations, means, standard deviations, minimums, maximums, and 95% confidence intervals. Change from baseline will be included using these same descriptive statistics.

For categorical variables such as mortality and NYHA classification, results will be summarized with subject counts and percentages/rates, and with 95% confidence intervals.

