12.8 Follow-up Compliance

The Sponsor will work with investigational sites to maintain high follow-up compliance. The following strategies may be used for increasing compliance:

- During site initiation and training, the Sponsor will emphasize the importance of subject follow-up to the site, and that the site should communicate this importance to each subject.
- Sites will be informed to promptly reschedule any missed subject visits, and to reinforce the necessity of a follow-up visit.
- If a scheduled visit is missed due to subject illness, transportation issues, or travel, the site will be advised to:
 - Reinforce the necessity of follow-up visits;
 - Identify alternate transportation sources, and involve the Sponsor if necessary
- Sites will be instructed to ask subjects who withdraw during the study to provide the reason for withdrawal and ask them if the investigator may contact them at the end of the study follow-up.
- Subject follow-up rates will be monitored closely so that problems may be identified and addressed as soon as possible.
- For subjects who are lost-to-follow-up, sites may be requested to examine the Social Security Death Index to determine subject status (only the status will be sent to Sponsor, not any subject identifying information).

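### Section 5.3 takes withdrawn subjects' vital status from a death index, which cannot establish that anyone is alive, and no rule keeps a non-match from counting as survival in the 5-year mortality summary

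*Combined protocol and SAP*

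**What the plan says.** Section 5.3 (Subject Discontinuation) closes data collection at withdrawal: "No additional follow-up will be required or data recorded from subjects once withdrawn from the study". The sentence then makes a single carve-out, for vital status: "except for the status (deceased/alive), which will be obtained from the Social Security Death Index". That is one named source, stated as mandatory, with two possible values.

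The same section makes one further provision. If the withdrawal is due to problems with the safety or performance of the device, "the investigator shall ask for the subject's permission to follow his/her status/condition outside of the clinical investigation".

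Section 12.8 (Follow-up Compliance) lists strategies that may be used. For subjects lost to follow-up, "sites may be requested to examine the Social Security Death Index to determine subject status". This is optional, and 12.8 does not itself use the two-valued wording. For subjects who withdraw, sites are to "ask them if the investigator may contact them at the end of the study follow-up".

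The endpoint concerned is in Section 3.2: "Freedom from all-cause mortality at 3 months, 6 months, 1 year, and then annually through 5 years post index procedure". Section 10.2.7 treats mortality as a categorical variable: "results will be summarized with subject counts and percentages/rates, and with 95% confidence intervals". Section 10.2.9 analyses all available data and does not impute missing values. Section 10.2.4 bases the analysis on subjects with an attempted implant, up to 30 of them (Section 4.2).

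**The concern.** A match in a death index is evidence of death. A non-match has several explanations: the subject is alive, the death is not yet listed, it was never listed, or the identifiers did not match. A field that allows only deceased or alive has no place for this uncertainty, so the natural entry for a non-match is alive.

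The evidence required also weakens at the moment a subject leaves. For subjects still in the study who miss a visit, Section 8.2 documents status by contacting them remotely. The note in Section 5.3.1 does not accept word from a relative or general practitioner as contact with the subject. After withdrawal, absence from a list would be enough.

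What is at stake is late survival. Reduced mortality is named as a potential benefit in Sections 2.4.1 and 16.1, and 2.4.1 says the results may be the basis for later protocols. If leavers tend to be sicker, which the documents do not address, missed deaths would be concentrated among them.

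**Working it through.** The documents state no mortality rate, withdrawal rate or index completeness, so there is no figure of the plan's own to reproduce. The check has four steps.

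**1. Can the value alive reach the endpoint?** Section 5.3 has the status recorded. Section 10.2.9 leaves data out only when they could not be collected, so a recorded alive is available data. Section 10.2.7 reports percentages or rates, with no time-to-event method, censoring rule or denominator. The value can therefore enter as survival, and nothing stops it. Nothing requires it either: the text does not say whether status after withdrawal is used at all.

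**2. Size per case.** With N = 30, one missed death coded alive adds 1/30 = 3.3 points to survival. With fewer registered subjects it adds more.

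**3. Spread between the codings left open.** The assumed example has 30 subjects and 9 known deaths, with 3 or 5 withdrawn subjects for whom no record is found. The intervals are exact 95% intervals; Section 10.2.7 does not name the type.

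| Coding of non-matches | 3 non-matches | 5 non-matches |
|---|---|---|
| Alive | 21/30 = 70.0% (50.6–85.3) | 21/30 = 70.0% (50.6–85.3) |
| Excluded as missing | 18/27 = 66.7% (46.0–83.5) | 16/25 = 64.0% (42.5–82.0) |
| Dead | 18/30 = 60.0% (40.6–77.3) | 16/30 = 53.3% (34.3–71.7) |

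*Expected overstatement of survival if coded alive* = 100 × w × q × (1 − s) / 30 points. Here w is the number who exit, q their risk of death by 5 years and s the share of deaths the index finds. All three are assumptions.

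- w = 1, q = 0.3, s = 0.9: 100 × 1 × 0.3 × 0.1 / 30 = 0.1
- w = 3, q = 0.5, s = 0.7: 100 × 3 × 0.5 × 0.3 / 30 = 1.5
- w = 5, q = 0.5, s = 0.5: 100 × 5 × 0.5 × 0.5 / 30 = 4.2
- w = 9, q = 0.6, s = 0.5 (all three extreme): 100 × 9 × 0.6 × 0.5 / 30 = 9.0

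**4. Would it be enough to keep index deaths and drop non-matches?** Assume 30% mortality among subjects who stay.

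- *w = 3, q = 0.3, s = 0.95.* True deaths are 27 × 0.3 + 3 × 0.3 = 9.0, so true mortality is 30.0%. Known deaths are 8.1 + 0.855 = 8.955. Coding non-matches alive gives 8.955/30 = 29.85%, an error of −0.15 points. Dropping the 3 − 0.855 = 2.145 non-matches gives 8.955/27.855 = 32.1%, an error of +2.1.
- *w = 6, q = 0.5, s = 0.7.* True deaths are 24 × 0.3 + 6 × 0.5 = 10.2, so true mortality is 34.0%. Known deaths are 7.2 + 2.1 = 9.3. Coding alive gives 9.3/30 = 31.0%, an error of −3.0. Dropping the 6 − 2.1 = 3.9 non-matches gives 9.3/26.1 = 35.6%, an error of +1.6.

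Dropping only the non-matches replaces one bias with the opposite one, so exits have to be handled symmetrically.

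**The case against.** The strongest reply is that the plan contains no rule scoring an undetected death as survival. A reader might infer such a rule from the two-valued wording in Section 5.3, but no section says how a non-match is coded, when the subject is censored, or whether the value enters the endpoint. Under Section 10.2.9 a non-match could equally be treated as missing, and Section 10.1 defers detail to an SAP. This stands: the bias is a risk that the text leaves open, not a stated method.

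A reader might also infer that the error can only flatter the device. That holds for a missed death, but a false match would record a living subject as dead.

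Nor would the problem be wholly invisible. Section 10.2.2 reports discontinuations with reasons and 10.2.1 provides subject listings, so with at most 30 subjects a careful reader could rebuild a worst case. A subject entered as alive would still not appear in any count of missing status.

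There are safeguards. Section 5.3.1 requires at least two calls or e-mails and then a certified letter before a subject is classed as lost. Section 12.8 raises contact at the end of follow-up, and 5.3 seeks permission to follow device-related withdrawals. These reduce the problem without closing it: the 12.8 contact is one of several optional strategies and is not tied to mortality, and the follow-up under 5.3 lies outside the investigation.

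Finally, the consequences are limited. Section 10.1 tests no hypothesis, Section 3 sets no pass or fail criterion, and the primary endpoint is at 30 days.

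**Conclusion.** The concern holds in a limited form. Section 5.3 asks a death index for a value it cannot supply, and nothing prevents a non-match from being counted as survival in the 5-year summary. The one firm figure is 3.3 points of survival per missed death at N = 30. The expected total is 0.1 to 4.2 points for 1 to 5 exits, a 30–50% risk of death among them and 50–90% index completeness; it reaches 9.0 points only when all three assumptions are pushed to the extreme shown above. None of these inputs comes from the documents.

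They do not support saying that the plan counts undetected deaths as survivors, or that the 5-year figure will be biased. The matter deserves correction because late survival may inform later protocols and the change is small. It does not threaten the 30-day primary endpoint.

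**What to change.** - **Coding.** In Section 5.3, replace the two values with three: *death record found*, *no death record found*, *confirmed alive by contact*. Apply the same coding to the subject status obtained under Section 12.8.
- **Positive evidence of life.** Use the permission for contact at the end of follow-up, already in 12.8, to confirm vital status where the subject agrees. This will help less for subjects who are lost.
- **Main estimate.** In Section 10.2.7, specify a time-to-event estimate. Censor every withdrawn or lost subject at the last direct contact before exit, whatever the index or a later contact shows. Do not keep index deaths while dropping non-matches.
- **Reporting.** State how many subjects have unverified status at each time point. Add a sensitivity range that includes index deaths and confirmed-alive contacts, and counts the unverified first all as alive and then all as dead.

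The cost is short edits to 5.3, 12.8 and 10.2.7, one eCRF code list and a little more analysis. The late survival figure may be wider or slightly less favourable. Censoring at exit still assumes that leavers resemble those who stay, which is why the range should appear beside it.
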